10.2 Source Documents

All study specific information obtained at each study visit must be recorded in the subject's record (source documentation), and then entered into a validated EDC database by trained site personnel. The source documentation may consist of source notes captured by site personnel in laboratory reports, ECG reports, and electronic source data.

10.3 Case Report Forms

Subject data required by this protocol are to be recorded in an EDC system on eCRFs and/or captured electronically by data vendors. The Investigator and his or her site personnel will be responsible for completing the eCRFs. The Investigator is responsible for the accuracy and reliability of all the information recorded on the eCRFs. All information requested on the eCRFs needs to be supplied, including subject identification data, visit date(s), assessment values, etc., and any omission or discrepancy will require explanation. All information on eCRFs must be traceable to source documentation (unless eCRF is considered the source) at the site.

10.4 Confidentiality

The Investigator must ensure that each subject's anonymity is maintained as described below. On the eCRFs, medical records, or other documents submitted to the Sponsor or designees, subjects must be identified by a subject identification number only. Subject identifiers uniquely identify subjects within the study and do not identify any person specifically. Documents that are not for submission to the Sponsor or designees (e.g., signed ICFs) should be kept in strict confidence by the Investigator in compliance with Federal regulations or other applicable laws or ICH guidance on GCP. Data collection and handling should comply with the European Union General Data Protection Regulation (EU GDPR) and other relevant regulations concerning data privacy, where applicable. Acadia has assigned a Data Protection Officer (DPO) as per the EU GDPR.

10.5 Study Records Retention

Investigators are required to maintain all essential study documentation as per ICH GCP guidelines. This includes, but is not limited to, copies of signed, dated and completed eCRFs, documentation of eCRF corrections, signed ICFs, audio recordings, subject-related source documentation, and adequate records for the receipt and disposition of all study drug. Investigators should maintain all essential study documentation, for a period of at least 2 years following the last approval of marketing application in an ICH region (US, Europe,

Final Version: 1.0 Clinical Study Protocol Amendment 4 Date: 21 December 2022

and Japan), or until at least 2 years after the drug investigational program is discontinued, unless a longer period is required by applicable law or regulation. Only the Sponsor can notify an Investigator or vendor when any records may be discarded. Investigators should contact the Sponsor before destroying any files.

10.6 Protocol Exceptions and Deviations

No prospective entry criteria protocol deviations are allowed; all subjects must meet all eligibility criteria in order to participate in the study.

Protocol waivers for eligibility will not be granted by the Sponsor under any circumstances. If, during the course of a subject's post-enrollment participation in the trial it is discovered that the subject did not meet all eligibility criteria, this will be reported as a major protocol deviation and not a waiver. In this situation, the subject will be discontinued, unless the discontinuation presents an unacceptable medical risk. The justification to allow the subject to continue in the trial will be made by the Sponsor, with medical input from the Investigator, and will be documented. All follow-up safety assessments must be completed and documented as outlined in the protocol (Section 6.7). The Investigator must report any protocol deviation to the Sponsor and, if required, to the IRB/EC in accordance with local regulations, within reasonable time.

10.7 Protocol Amendments

Changes to the protocol may be made only by the Sponsor (with or without consultation with the Investigator). All protocol modifications must be submitted to the site IRB/EC in accordance with local requirements and, if required, to regulatory authorities, as either an amendment or a notification. Approval for amendments must be awaited before any changes can be implemented, except for changes necessary to eliminate an immediate hazard to trial subjects, or when the changes involve only logistical or administrative aspects of the trial. No approval is required for notifications.

11 QUALITY MANAGEMENT

11.1 Risk Management

The Sponsor utilizes the ICH E6 (GCP) Revision 2 risk management approach that includes methods to assure and control the quality of the trial proportionate to the risks inherent in the trial and the importance of the information collected. The intent is that all aspects of this trial are operationally feasible and that any unnecessary complexity, procedures, and data collection are avoided. The Sponsor's risk management approach includes the following documented activities:

Study: ACP-103-069 Clinical Study Protocol Amendment 4 Date: 21 December 2022

• Critical Process and Data Identification: during protocol development, risks of processes and data that are critical to ensure human subject protection and the reliability of trial results are identified and assessed.

- Risk Identification: risks to critical trial processes, governing systems, investigational product, trial design, data collection, and recording are identified.
- Risk Evaluation: identified risks are evaluated by considering the following factors: (a) likelihood of occurrence, (b) impact on human subject protection and data integrity, and (c) detectability of errors.
- Risk Control: risks that can be avoided, reduced (i.e., mitigated), or accepted are differentiated. Risk mitigation activities are incorporated in protocol design and implementation, study plans, training, processes, and other documents governing the oversight and execution of study activities. Where possible, predefined quality tolerance limits are defined to identify systematic issues that can impact subject safety or data integrity and deviations from the predefined quality tolerance limits will trigger an evaluation and possibly an action. Contingency plans are developed for issues with a high risk factor that cannot be avoided.
- Periodic risk review, communication, and escalation of risk management activities during trial execution and risk outcome reporting in the clinical study report (CSR).

11.2 Quality Control and Quality Assurance

The Sponsor or designees and regulatory authority inspectors are responsible for contacting and visiting the Investigator for the purpose of inspecting the facilities and, upon request, inspecting the various records of the trial (e.g., eCRFs and other pertinent data) provided that subject confidentiality is respected.

The Sponsor's or designee's monitor is responsible for inspecting the eCRFs at regular intervals throughout the study to verify adherence to the protocol; completeness, accuracy, and consistency of the data; and adherence to local regulations on the conduct of clinical research. The monitor should have access to subject medical records and other study-related records needed to verify the entries on the eCRFs.

The Investigator agrees to cooperate with the monitor to ensure that any problems detected in the course of these monitoring visits are resolved.

In accordance with ICH guidance on GCP and the Sponsor's audit plans, sites participating in this study may be audited. These audits may include a review of site facilities (e.g., pharmacy, drug storage areas, and laboratories) and review of study-related records may

Final Version: 1.0

Final Version: 1.0 Clinical Study Protocol Amendment 4 Date: 21 December 2022

occur in order to evaluate the trial conduct and compliance with the protocol, ICH guidance on GCP, and applicable regulatory requirements.

The Sponsor's or designee's representatives, regulatory authority inspectors and IRB/EC representatives who obtain direct access to source documents should also respect subject confidentiality, taking all reasonable precautions in accordance with applicable regulatory requirements to maintain the confidentiality of subjects' identities.

12 ETHICAL CONSIDERATIONS

12.1 Ethical Standard

The study will be conducted in compliance with the protocol, the Declaration of Helsinki, ICH GCP, and other applicable regulatory requirements (e.g., Serious Breach reporting, urgent safety measures, and European Union General Data Protection Regulation [EU GDPR]).

The study will be performed in accordance with current US Health Insurance Portability and Accountability Act (HIPAA) regulations, US FDA GCP Regulations (US CFR 21 parts 50, 54, 56, and 312), and ICH guidance on GCP (E6) and clinical safety data management (E2A).

In accordance with Directive 75/318/EEC, as amended by Directive 91/507/EEC, the final clinical study report will be signed by an Investigator and/or Coordinating Investigator who will be designated prior to the writing of the clinical study report.

12.2 Institutional Review Board/Ethics Committee

The Investigator or designee will provide the IRB/EC with all requisite material, including a copy of the protocol, informed consent, any subject information or advertising materials, and any other requested information. The study will not be initiated until the IRB/EC provides written approval of the protocol and the informed consent and until approved documents have been obtained by the Investigator and copies received by the Sponsor. All amendments will be sent to the IRB/EC for information (minor amendment) or for submission (major amendment) before implementation. The Investigator will supply the IRB/EC and the Sponsor with appropriate reports on the progress of this study, including any necessary safety updates, in accordance with the applicable government regulations and in agreement with policy established by the Sponsor.

12.3 Informed Consent/Assent Process

Properly executed, written informed assent/consent must be obtained from each subject and/or subject's parent/LAR prior to any screening procedures.

The informed consent must, at a minimum, include the elements of consent described in the ICH guidance on GCP and the US CFR 21 part 50.25. A copy of the ICF planned for use will be reviewed by the Sponsor or designee for acceptability and must be submitted by the Investigator or designee together with the protocol, to the appropriate IRB/EC for review and approval prior to the start of the study at that investigational site. Consent forms must be in a language fully comprehensible to the prospective subject and their parent/LAR. The Investigator must provide the Sponsor or designee with a copy of the IRB/EC letter approving the protocol and the ICF before the study drug supplies will be shipped and the study can be initiated.

The consent form must be revised if new information becomes available during the study that may be relevant to the subject's willingness to continue participation. Any revision must be submitted to the appropriate IRB/EC for review and approval in advance of use.

12.3.1 Subject Assent Form

To participate in the study, the subject will assent to an understanding of, and sign the assent form. The subject will be made aware of the ability to withdraw from the study at any time, without prejudice. The subject's assent for participation must be documented. Assent is the affirmative agreement to participate in the research of a minor. If the subject cannot sign the form, a witness will be allowed to provide written verification of oral assent.

12.3.2 Parent and Legally Acceptable Representative Informed Consent

Written informed consent will be obtained from the subject's parent/LAR before the subject participates in any study-related procedure. To provide consent for the subject's participation in the study, the subject's parent/LAR will read, assent to an understanding of, and sign an ICF or other locally applicable regulations and authorization form after having had an opportunity to discuss the forms with the Investigator. The parent/LAR will be made aware that the subject may withdraw from the study at any time and will receive a copy of the signed ICF. Subjects who reach the age of majority (i.e., 18 years in most jurisdictions) during the course of the study are required to be re-consented.

12.3.3 Consent and Other Informational Documents Provided to Subjects

The subject and/or parent/LAR must be given a copy of the signed informed consent and the original maintained in the designated location at the site.

12.3.4 Consent Procedures and Documentation

It is the Investigator or designee's responsibility to obtain written informed consent from the subject and/or parent/LAR after adequate explanation of the aims, methods, anticipated benefits, and potential hazards of the study. The subject and/or parent/LAR must be given

Final Version: 1.0

ample time to decide about study participation and opportunity to inquire about details of the study. The IRB/EC-approved consent form must be personally signed and dated by the subject or parent/LAR with subject assent and by the person who conducted the informed-consent discussion. The Investigator or appropriate site personnel must document the details of

Final Version: 1.0

Date: 21 December 2022

Records related to a study subject's participation will be maintained and processed according to local laws, and where applicable, the European Union General Data Protection Regulation (EU GDPR). The consent and study information documentation will include statements describing local and regional requirements concerning data privacy, and who to contact for questions.

12.3.4.1 Remote Consent Procedures and Documentation

obtaining informed consent in the subject's study documents.

In exceptional circumstances, and with the approval of the Medical Monitor, Investigators may obtain informed consent from the subject or parent/LAR when these individuals are unable to travel to the site where the Investigator is located due to extenuating circumstances (e.g., pandemic, natural disaster, or political upheaval). This is only permitted when a new consent is approved by the IRB/EC and the subject and/or parent/LAR need to be re-consented. The consent form may be sent to the subject or the subject's parent/LAR by facsimile or e-mail, and the consent interview may then be conducted by telephone when the subject or subject's parent/LAR can read the consent form during the discussion. After the consent discussion, the subject or the subject's caregiver can sign and date the consent form. Options for returning the document to the clinical Investigator may include facsimile, scanning the consent form and returning it through a secure e-mail account, or posting it to a secure internet address. Alternatively, the subject or caregiver may bring the signed and dated consent form to his/her next visit to the clinical site, if restrictions on traveling to the clinical trial site are alleviated, or mail it to the clinical Investigator. The case history for each subject must document that informed consent was obtained prior to conducting any assessments at the visit the re-consent was conducted. The Investigator should have the subject and/or parent/LAR confirm verbally during the consent interview that the subject and/or parent/LAR has signed and dated the form. In addition, the person signing the consent form must receive a copy of the consent form.

13 PUBLICATION PLAN

All publication rights are delineated in the Clinical Study Agreement and/or other separate agreements with the Investigator and/or Institution, as applicable.

14 CONFLICT OF INTEREST POLICY

14.1 Finance, Insurance, and Indemnity

Arrangements for finance, insurance, and indemnity are delineated in the Clinical Study Agreement and/or other separate agreements with the Investigator and/or Institution, as applicable.

16 APPENDICES

Appendix A Prohibited and Restricted Medications^a

Subjects taking prohibited medications at study entry will not be eligible for the study.

Subjects who require current treatment with a prohibited medication will be withdrawn from the study.

Subjects who have previously taken a prohibited medication during the study will be withdrawn from the study unless:

- the prohibited medication has been discontinued AND
- withdrawal from the study presents an unacceptable medical risk to the subject

The justification to allow the subject to continue in the trial will be made by the Sponsor/Medical Monitor with medical input from the Investigator, and will be documented. If allowed to remain in the trial, this will be reported as a major protocol deviation and not a waiver.

The table below lists prohibitions and restrictions by medication class, including representative medications within class. A **prohibited** medication is not allowed. A **restricted** medication is allowed only under certain conditions.

Medication Class	Medication ^a	Prohibition/restrictions
Antiarrhythmic	PROHIBITED	Prohibited at study entry and throughout the treatment
drugs	• ajmaline	period
	• amakalant, semantilide	
	 amiodarone 	
	• bretylium	
	 disopyramide 	
	• dofetilide	
	• dronedarone	
	• flecainide	
	• ibutilide	
	• procainamide	
	• propafenone	
	• quinidine	
	• sotalol, d-sotalol	
Anticholinergics	PROHIBITED	Centrally acting anticholinergic medications are
	Centrally acting	prohibited throughout the treatment period and must be washed out and discontinued at least 2 weeks or 5
	anticholinergics	half-lives (whichever is longer) prior to Baseline
	o biperiden	

Medication Class	Medicationa	Prohibition/restrictions
	0 trihexiphenidyl	
	RESTRICTED o benztropine o oral diphenhydramine	 Benztropine (≤6 mg/day) is allowed for movement disorders Oral diphenhydramine is allowed at ≤50 mg per day for acute extrapyramidal symptoms
	 UNRESTRICTED peripherally acting anticholinergics topical diphenhydramine 	Peripherally acting anticholinergic medications and topical diphenhydramine are allowed without restriction
Anticonvulsant and mood stabilizers	 PROHIBITED carbamazepine lamotrigine lithium oxcarbazepine phenytoin valproate 	 Must be washed out at least 2 weeks or 5 half-lives (whichever is longer) prior to Baseline Prohibited throughout the treatment period If subject has a history of seizures, must be seizure-free and off epileptic drugs for at least 6 months prior to Screening
Antidepressants	PROHIBITED amitriptyline citalopram clomipramine desipramine desvenlafaxine doxepin duloxetine escitalopram esketamine fluvoxamine imipramine ketamine mianserin mirtazapine nefazadone nortriptyline sertraline trazodone trimipramine	 Prohibited throughout the treatment period Must be discontinued at least 2 weeks or 5 half-lives (whichever is longer) prior to the Baseline visit

Final Version: 1.0 Date: 21 December 2022

Medication Class	Medication ^a	Prohibition/restrictions
	• venlafaxine	
Antimanic agents	PROHIBITED • lithium • valproate	Prohibited at study entry and throughout the treatment period
Antimicrobials, antifungals, and antimalarials	PROHIBITED clarithromycin erythromycin levofloxacin moxifloxacin pentamidine roxithromycin	Prohibited at study entry and throughout the treatment period
	RESTRICTED artenimol/piperaquine azithromycin bedaquiline ciprofloxacin fluconazole gemifloxacin norfloxacin ofloxacin telavancin telithromycin	 Prohibited at Baseline but may be used during the course of the study to treat a bacterial infection (e.g., urinary tract infection, respiratory infection), post-Baseline at the discretion of the Investigator These restricted medications are only allowed under the following conditions: The subject has a Baseline ECG with a QTcF 425 ms IF QRS duration is < 120 ms OR The subject has a QTcF < 450 ms at Baseline IF QRS duration ≥120 ms
Antipsychotics other than pimavanserin	PROHIBITED All in class	 Must be washed out 2 weeks or 5 half-lives (whichever is longer) prior to Baseline Prohibited throughout the treatment period
Anxiolytics	PROHIBITED • chlordiazepoxide • diazepam • flurazepam	Prohibited at study entry and throughout the treatment period
	RESTRICTED alprazolam lorazepam midazolam oxazepam temazepam triazolam	• Mild sedation is allowed exceptionally for ECGs and blood draws during the study (e.g., alprazolam at a pediatric-appropriate dose per age, and the lowest dose deemed necessary by the Investigator) just in cases when the subject's agitation/anxiety does not allow a safe and accurate measurement and the Investigator, with agreement from the caregiver, considers it safe and appropriate for the subject.

Final Version: 1.0 Date: 21 December 2022

Medication Class	Medicationa	Prohibition/restrictions
		 Short- or medium-acting benzodiazepine may be used for acute anxiety May not be used within 12 hours prior to an assessment visit Lorazepam, in doses according to age, may be used as a rescue medication for a maximum of 7 consecutive days. Reassessment and discussion with Medical Monitor is required if needed beyond 7 days. If lorazepam is not available, another benzodiazepine from the restricted list may be used
Beta blockers	PROHIBITED • propranolol	Prohibited at study entry and throughout the treatment period
Centrally-acting alpha-agonist hypotensive agents	PROHIBITED • clonidine	Prohibited at study entry and throughout the treatment period
Centrally-acting alpha _{2A} adrenergic receptor agonists	PROHIBITED • guanfacine	Prohibited at study entry and throughout the treatment period
Hypnotics and sleeping agents	PROHIBITEDeszopiclonezolpidemzopiclone	Prohibited at study entry and throughout the treatment period
	RESTRICTED • melatonin • ramelteon • zaleplon	May not be used within 12 hours of a cognitive assessment, and efforts should be made to limit agents to lowest dose for the shortest time needed. ○ Melatonin is allowed (≤5 mg/day) for insomnia
Non-stimulant ADHD medications	RESTRICTED • atomoxetine	Allowed if stable for at least 12 weeks prior to Screening and the dose is expected to remain the same throughout the duration of the study
Opioids	PROHIBITED • methadone	Prohibited at study entry and throughout the treatment period
Serotonin antagonists	PROHIBITED • cyproheptadine	 Prohibited throughout the treatment period Must be discontinued at least 3 weeks prior to the Baseline visit
Stimulants and wake-promoting agents	RESTRICTEDamphetamine saltsarmodafinil	Allowed if stable for at least 12 weeks prior to Screening and the dose is expected to remain the same throughout the duration of the study

Final Version: 1.0 Date: 21 December 2022

Medication Class	Medicationa	Prohibition/restrictions
	• lisdexamfetamine	
	 methylphenidate 	
	• modafinil	

Final Version: 1.0

Date: 21 December 2022

Abbreviations: ADHD=attention-deficit hyperactivity disorder; ECG=electrocardiogram; QTcF=corrected QT interval using Fridericia's correction method; QRS=QRS interval on ECG;

^a Medications within each class include but are not limited to the examples listed in this table.

Appendix B Prohibited and Restricted Concomitant Medications: Inhibitors and Inducers of Cytochrome P450 Enzyme 3A4

The information presented here is intended to provide guidance and does not constitute an exhaustive list of strong CYP 3A4 enzyme (CYP3A4) inhibitors and inducers. Any questions should be discussed with the Medical Monitor or appropriate designee.

Subjects who require current treatment with a prohibited medication will be withdrawn from the study.

Subjects who have previously taken a prohibited medication during the study will be withdrawn from the study unless:

- the prohibited medication has been discontinued AND
- withdrawal from the study presents an unacceptable medical risk to the subject

The justification to allow the subject to continue in the study will be made by the Sponsor/Medical Monitor with medical input from the Investigator, and will be documented. If allowed to remain in the study, this will be reported as a major protocol deviation and not a waiver.

The metabolism of pimavanserin is affected by strong CYP3A4 inhibitors, resulting in an increase in maximum plasma concentration (C_{max}) and area under the plasma concentration-time curve (AUC) of approximately 3-fold.

Strong inhibitors of CYP3A4 are to be stopped at least 2 weeks or 5 half-lives prior to investigational product administration, whichever is longer. Strong inducers of CYP3A4 are to be stopped 30 days or 5 half-lives prior to investigational product administration, whichever is longer. Moderate inhibitors and inducers of CYP3A4 are allowed but should be used with caution.

STRONG	grapefruit juice ^a	MODERATE	grapefruit juice ^a
INHIBITORS	boceprevir (Victrelis®)	INHIBITORS	amprenavir (Agenerase®)
	clarithromycin (Biaxin®)		aprepitant (Emend®)
	cobicistat (part of Stribild®)		atazanavir (Reyataz®)
	indinavir (Crixivan®)		ciprofloxacin (Cipro®)
	itraconazole (Sporanox®)		conivaptan (Vaprisol®)
	ketoconazole (Nizoral®)		crizotinib
	lopinavir and ritonavir (Kaletra®)		cyclosporine
	mibefradil (Posicor®)		darunavir/ritonavir
	nefazodone (Serzone®)		(Prezista®/Ritonavir)
	nelfinavir (Viracept®)		diltiazem
	posaconazole (Noxafil®)		dronedarone
	quinupristin (Synercid®)		erythromycin (Erythrocin®
	ritonavir (Norvir®, part of Viekira		Lactobionate)

	Pak TM) - combination treatments including ritonavir, such as: danoprevir and ritonavir elvitegravir and ritonavir indinavir and ritonavir lopinavir and ritonavir paritaprevir and ritonavir and ombitasvir(and/or dasabuvir)		fluconazole (Diflucan®) fluvoxamine (Luvox®) fosamprenavir (Lexiva®) imatinib (Gleevec®) isavuconazole tofisopam verapamil (Calan®)
	saquinavir and ritonavir tipranavir and ritonavirsaquinavir (Invirase®) telaprevir (Incivek®) telithromycin (Ketek®) troleandomycin voriconazole (Vfend®)		
STRONG INDUCERS	apalutamide avasimibe carbamazepine (Tegretol®) enzalutamide ivosidenib lumacaftor mitotanephenytoin (Dilantin®) rifampin (Rifadin®, Rifadin® IV, Rimactane®) St. John's Wort	MODERATE INDUCERS	bosentan (Tracleer®) cenobamate dabrafenib efavirenz (Sustiva®) etravirine (Intelence®) lorlatinib modafinil (Provigil®) nafcillin (Unipen®, Nallpen®) pexidartinib phenobarbital (Luminal®, Solfoton®) primidone sotorasib

Final Version: 1.0

The effect of grapefruit juice varies widely among brands and is concentration-, dose-, and preparation-dependent. Studies have shown that it can be classified as a "strong CYP3A inhibitor" when a certain preparation was used (e.g., high dose, double strength) or as a "moderate CYP3A inhibitor" when another preparation was used (e.g., low dose, single strength). (FDA Drug Development and Drug Interactions http://www.fda.gov/Drugs/DevelopmentApprovalProcess/DevelopmentResources/DrugInteractionsLabelin g/ucm093664.htm#classInhibit).

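### Appendix A permits telithromycin after Baseline, but Appendix B lists it as a strong CYP3A4 inhibitor, a class the protocol prohibits

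*Protocol*

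**What the plan says.** **Appendix A, antimicrobials row.** The restricted list ends with "norfloxacin ofloxacin telavancin telithromycin". Drugs on that list are barred at Baseline but "may be used during the course of the study to treat a bacterial infection", post-Baseline, at the Investigator's discretion. The row continues: "These restricted medications are only allowed under the following conditions". The conditions are a Baseline QTcF limit of 425 ms when QRS is under 120 ms (the comparison sign was lost in text extraction), or a Baseline QTcF below 450 ms when QRS is 120 ms or more. The prohibited list in the same row reads "clarithromycin erythromycin levofloxacin moxifloxacin pentamidine roxithromycin".

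**Appendix B.** Telithromycin stands in the strong-inhibitor column, as does clarithromycin. The rule begins "Strong inhibitors of CYP3A4 are to be stopped at least" and goes on to require two weeks or five half-lives before study drug, whichever is longer. Only moderate inhibitors and inducers are allowed, with caution. The stated effect of strong inhibitors is a rise in Cmax and "area under the plasma concentration-time curve (AUC) of approximately 3-fold".

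**Section 4.2, exclusion 1** names strong CYP3A4 inhibitors among the prohibited medications. **Section 4.8.2.1** applies both appendices from the screening visit to Visit 8 or early termination. It requires withdrawal after prohibited use, unless the drug has been stopped and withdrawal would itself be an unacceptable medical risk.

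**The concern.** Two operative lists give opposite answers for one drug. An Investigator treating an infection who looks up telithromycin in Appendix A finds an express permission with QT conditions attached. Appendix B bars the class, and nothing says which appendix wins.

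The matter is one of safety. Section 1.5.1 says that pimavanserin prolongs the QT interval, and that adolescents showed dose-related QTc prolongation and a trend to higher exposure at lower age and weight. Section 1.4.2 explains that children aged 5 to 12 receive lower doses because Cmax at 34 mg rises as age and weight fall. An unplanned rise in exposure is what the dosing scheme tries to avoid.

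Handling may also differ between sites. The same prescription is permitted under Appendix A but leads to withdrawal or a major deviation under Appendix B.

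**Working it through.** The plan gives no figure to reproduce here. The check compares the lists and asks whether the bar applies during treatment.

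**1. Strong agents named in both appendices**

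| Drug | Appendix A | Appendix B |
|---|---|---|
| clarithromycin | prohibited | strong inhibitor |
| nefazodone (spelled nefazadone in Appendix A) | prohibited | strong inhibitor |
| telithromycin | restricted, allowed after Baseline | strong inhibitor |
| carbamazepine | prohibited | strong inducer |
| phenytoin | prohibited | strong inducer |

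Appendix A prohibits 2 of the 3 strong inhibitors. Adding the inducers gives 2 + 2 = 4 of 5. Telithromycin is the only exception, and no reason is given for it.

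**2. Restricted antimicrobials against Appendix B**

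The restricted list has 10 entries. One is strong in Appendix B (telithromycin). Two are moderate (ciprofloxacin and fluconazole), so their restricted status is consistent with Appendix B. The other 10 − 1 − 2 = 7 do not appear there.

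**3. Does the bar reach beyond entry?**

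Exclusion 1 is an entry criterion, and Appendix B's timing rule is a washout before dosing. Taken alone, neither settles use after Baseline. However, Section 4.8.2.1 carries the prohibitions through Visit 8 or early termination, Appendix B allows only moderate inhibitors, and Appendix B repeats the withdrawal rule for prohibited use during the study. The bar therefore holds during treatment.

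**4. Does Appendix A's ECG condition cover the interaction?**

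Table S-1 requires all assessments to be complete before randomization, and Section 5.1.3 places the first dose at the Baseline visit. The Baseline ECG is therefore taken before any study drug. It can limit pre-existing QT prolongation, but it cannot detect a later rise in pimavanserin exposure. Section 6.4.4 schedules later ECGs only at Weeks 3 and 6, the minimum list for unscheduled visits in Section 6.8 has no ECG, and starting a restricted antimicrobial does not trigger one.

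**5. Scale of the exposure effect**

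Take the protocol's 3-fold figure and assume dose-proportional exposure. Section 1.3.2 supports this approximately from 10 to 34 mg in adolescents after weight adjustment; beyond 34 mg it is extrapolation. The equivalent doses without an inhibitor are then:

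- 10 mg × 3 = 30 mg/day
- 20 mg × 3 = 60 mg/day
- 34 mg × 3 = 102 mg/day

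This is the full steady-state effect. With the 57-hour half-life in Section 1.3.2, five half-lives take 5 × 57 = 285 hours, or 285 / 24 ≈ 12 days, and longer if inhibition slows elimination. A shorter course would probably fall short of 3-fold.

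**The case against.** The best counter-argument is that the appendices already apply together. Section 4.8.2.1 cites both, Section 4.8.2 sends treatment of adverse events to both, and Appendix A treats a restricted drug as one allowed only under conditions, which need not exempt it from Appendix B. The lists also conflict in the other direction: Appendix A prohibits erythromycin, dronedarone and fluvoxamine, although Appendix B classes them as moderate inhibitors, which it allows. No sensible site would take Appendix B as overriding Appendix A for those drugs.

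That reading is plausible, but no text states it, and the telithromycin row is an express permission. The three reverse cases err on the safe side. They show that telithromycin is not the only mismatch between the lists, and they make a precedence sentence more useful.

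Several safeguards do stand. The 425 ms limit leaves 450 − 425 = 25 ms below the entry limit, which gives some room for added QT effect from any cause. Subjects must consult the Investigator before taking any medication, except in an emergency. Questions go to the Medical Monitor, the Investigator may add safety evaluations, ECGs at Weeks 3 and 6 are centrally read, and a DSMB reviews safety. Section 1.3 reports multiple dosing up to 136 mg/day in healthy subjects, above the 102 mg/day equivalent, although those were not children with ASD. These points limit the size of the problem but do not remove the contradiction.

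**Conclusion.** The concern holds. Appendix A permits, for one drug, what Appendix B, exclusion 1 and Section 4.8.2.1 together prohibit. The pattern of the lists points to a slip rather than a considered exception.

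The conflict itself rests on the text alone. Its clinical size rests on the protocol's approximate 3-fold figure, which a short course may not reach, and on how often telithromycin would be prescribed. The documents do not give that frequency, and it is probably low. No effect on the primary estimate, alpha or power is claimed. The correction should be made because it concerns an operative rule for a QT-prolonging drug in children.

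The anticonvulsant washout is not a second conflict. Appendix A's two weeks or five half-lives for carbamazepine and phenytoin is a minimum, and Appendix B's 30 days satisfies it.

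**What to change.** 1. In Appendix A, move telithromycin from the restricted to the prohibited antimicrobials, next to clarithromycin.
2. In Section 4.8.2.1, add one sentence: when a medication appears in both Appendix A and Appendix B, the stricter rule governs. This also settles erythromycin, dronedarone and fluvoxamine.
3. Optionally, add a cross-reference to Appendix B at the anticonvulsant washout, for clarity only.

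The cost is one drug moved between two lists and one added sentence in the protocol. Assessments, sample size, analysis and the SAP do not change.
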